4.1.2 Study Design

Subjects will provide written informed consent prior to initiating any screening procedures. Subjects meeting all screening criteria will be eligible for enrollment and randomization into the study. Subjects with COVID-19 disease with signs and symptoms reported > 72 hours from onset will be given instructions to see their primary care physician or be advised to seek potential treatment (if eligible) at a local antibody infusion center.

This Phase II, dose finding portion of the trial is targeting to enroll a minimum of 60 volunteers with 30 in each of at least two dosing cohorts (20 assigned to RD-X19 and 10 assigned to sham per cohort, 2:1 randomization).

Cohort A will begin with 24 J/cm² per treatment, administered 2X/Day for duration of 7 days. Once 80% of subjects (n=24) in Cohort A complete the Day 8 visit and no predefined safety signals as outlined in the study pausing/stopping criteria have been observed, Cohort B, 32 J/cm² per treatment will start enrollment. In the event device-related serious adverse events or patterns of device-related adverse events, including application site reactions, are observed in Cohort A, and based on the review and recommendation of the external safety monitoring committee (SMC) of unblinded data, the study may proceed with enrollment and dosing in Cohort C, 16 J/cm² per treatment in keeping with SMC recommendations. An illustration of the ascending (or descending) dose finding design is provided below.

Cohort A: RD-X19 24 J/cm² vs. Sham

[figure not shown]
(5 minute treatment, 2X/Day for a duration of 7 days)

Cohort B: RD-X19 32 J/cm² vs. Sham

(5 minute treatment, 2X/Day for a duration of 7 days)

Cohort C: RD-X19 16 J/cm² vs. Sham

(5 minute treatment, 2X/Day for a duration of 7 days)

In the final Cohort to be investigated, once 80% of the subjects complete the Day 8 visit without observation of safety signals meeting the definition of predefined pausing/stopping criteria, a blinded review of available safety data for Cohort A and Cohort B will be conducted along with a blinded assessment of the proportion of 'success' events on the first primary endpoint of sustained symptom resolution for the subjects within each Cohort. At the sponsors option the final cohort enrollment may be increased in sample size (targeting up to an additional 150 subjects, 2:1 randomization). This option to increase overall enrollment is intended to provide better resolution of the point estimate between a safe, well tolerated dose and sham treatment in a broader population, including subjects who are SARS-CoV-2 Anti-Spike IgG antibody positive at Baseline, either through natural infection or immunization, in preparation for future trials. In the event safety signals are observed during the conduct of Cohort B (32 J/cm²), based on the review and recommendation of the SMC, the sponsor may elect to proceed with the optional additional enrollment and dosing in the initial Cohort A, 24 J/cm² per treatment. As such, the Final Cohort is defined as the cohort including the final randomized subject.

Subjects meeting all inclusion criteria and none of the exclusion criteria will be randomized in a 2:1 ratio within each dosing cohort. Light will be administered locally to the mouth and throat only, aiming to eliminate SARS-CoV-2 viral load in these targeted portions and surrounding tissues of the upper respiratory tract. Assessments of safety, and clinical outcomes will occur as outlined in Table 1 below. Clinic visits will occur post-baseline (Day 1) on study days 3, 5, 8, and 14 (+/-2, inclusive). Telephonic outreach by study personnel will occur on days 2 and 4 for additional safety monitoring and to enhance compliance with at-home study procedures. Study subjects requiring hospitalization will be tracked until discharge or death and the time and date of these events captured.

Study Subject safety will be monitored throughout the study by the Site Investigators, supported by regular review by the Sponsor's Chief Medical Officer and the CRO medical monitor with strict stopping criteria identified for discontinuation of dosing within a treatment arm.

Table 1: Objectives and Outcome Measures

| OBJECTIVES | ENDPOINTS (OUTCOME MEASURES) |
|--|---|
| Safety Assessments | |
| 
• Serious Adverse Events (SAEs) and Treatment Emergent Adverse Events (TEAEs) characterized by Medical Dictionary for Regulatory Affairs (MedDRA) System Order Classified (SOC) Preferred Terms (PTs), including application site local reactions and device-related TEAEs | 
• Collection and summary of all TEAEs reported from study subjects' daily diary cards or in office visits and via monitoring for application site reactions during clinic visits by investigators' examination of intraoral pathology. MedDRA SOC PT- |

| | |
|---|---|
| | 
defined TEAEs will be established and evaluated individually and collectively for severity and attribution and presented in tables and listings.
 |
| Primary Outcome Assessments | 
• Sustained resolution of COVID-19 signs and symptoms in all subjects (with mild or moderate disease at baseline)• Time to sustained resolution of COVID-19 signs and symptoms as measured by the time (in hours) when cough, sore throat, nasal congestion, headache, chills and or sweats, myalgia, fatigue, and nausea (with or without vomiting) have been assessed by the subject as none (0) or mild (1) and all symptoms remain at or below 1 until study Day 14. *Subjects reporting a persistent fever (100.5 degrees for 36 hours or more) and/or SpO₂ levels <96% with any shortness of breath fail to meet the success criterion on that day even if all other symptoms are reported as none (0) or mild (1). |
| 
• Sustained resolution of COVID-19 signs and symptoms in subjects with Mild disease at baseline | 
• Time to sustained resolution of COVID-19 signs and symptoms as measured by the time (in hours) when cough, sore throat, nasal congestion, headache, chills and or sweats, myalgia, fatigue, and nausea (with or without vomiting) have been assessed by the subject as none (0) or mild (1) and all symptoms remain at or below 1 until study Day 14. *Subjects reporting a persistent fever (100.5 degrees for 36 hours or more) |

| | |
|--|---|
| | and/or SpO ₂ levels <96% with any shortness of breath fail to meet the success criterion on that day even if all other symptoms are reported as none (0) or mild (1). |
| Secondary Clinical Outcome Assessments | |
| | 
• Day 8 Composite Resolution• Worsening of Disease• Return to Pre-COVID Health 
• Proportion of study subjects who achieve 'Day 8 Composite Resolution' defined as both a negative SARS-CoV-2 antigen test within the window for Visit 4 and all symptoms assessed by the subject as none (0) or mild (1), absence of fever and SpO₂ ≥96% without shortness of breath on study day 8.• Number and percentage of study subjects who experience progression of COVID-19 as defined by an increase of the composite COVID-19 severity score greater than baseline at any point in the study on or after day 3.• Numbers and percentages of study subjects on day 8 and day 14 who answer yes to the following patient-reported global impression assessments, a) return to usual health and b) return to usual activities.
a) In the past 24 hours, have you returned to your usual health (before your COVID-19 illness)? Yes or Nob) In the past 24 hours, have you returned to your usual activities (before your COVID-19 illness)? Yes or No• Numbers and percentages of study subjects who: |

| | |
|--|--|
| 
• Severe Clinical Outcomes | 
1) who require medical attention or intervention attributed to COVID-19;2) who progress to severe disease with respiratory rate >30/minute and/or O2 saturation $\leq 93\%$ on room air or FiO2 $\geq 300\%$ with any respiratory distress;3) who require hospitalization for severe COVID-19;4) who require endotracheal ventilation or ECMO with or without the use of solumedrol; and5) who die. |
| Secondary Virologic Outcome Assessments | |
| 
• Change in Nasopharyngeal VL• Clearance of viral shedding (undetectable SARS-CoV-2 VL) | 
• Mean change in nasopharyngeal VL from baseline on days 3, 5, 8, and 14.• Tabulated geometric mean nasopharyngeal VL at baseline and on Days 3, 5, 8 and 14.• Proportion of subjects demonstrating clearance of viral infection, defined as a negative nasopharyngeal swab via RT-qPCR as assessed on each of Days 3, 5, 8 and 14. |
| Exploratory Assessments | |
| 
• Change in oral microbiome | 
• Change in α and β diversity in microbial flora from baseline on day 8 and day 14 as analyzed by 16S rRNA subunit analysis from frozen saliva |

| | |
|---|--|
| 
• Change in Saliva VL | 
samples.
 
• Mean change in saliva VL on days 3, 5, 8, and 14.• Tabulated geometric mean saliva VL at baseline and on days 3, 5, 8 and 14. |
|---|--|

The study SAP will outline all study analytical tables and listings, by treatment assignment and whether analysis population is Safety/FAS, mFAS or PP.

4.2 Inclusion and Exclusion Criteria

A subject must meet all the following criteria to be eligible for **inclusion** in this study:

1. Positive for SARS-CoV-2 as detected using an FDA authorized SARS-CoV-2 antigen test at or within 24 hours of the screening visit.
2. COVID-19 signs and symptoms within 72 hours from symptom onset, including at least two moderate* or greater symptoms from: cough, sore throat, nasal congestion, headache, unexplained chills and/or sweats, myalgia, fatigue, nausea (with or without vomiting).
 - Subjects with the presence of at least one moderate symptom and either a) a fever with an oral temperature of at least 100.5 °F or b) shortness of breath/difficulty breathing on exertion (e.g., walking, going up and down stairs) are also eligible for enrollment.
3. BMI <40
4. Provides written informed consent prior to initiation of any study procedures.
5. Be able to understand and agrees to comply with planned study procedures and be available for all study visits.
6. Agrees to the collection of saliva, nasopharyngeal, and venous blood specimens per protocol.
7. Males or females, 18 to 65 years of age, inclusive.
8. No uncontrolled disease process(es) based on patient reported medical history (chronic or acute), other than direct COVID-19 signs and symptoms.
9. No physical or mental conditions or attributes at the time of screening, which in the opinion

of the PI, will prevent full adherence to, and completion of, the protocol.

*Symptom scoring is independent from the classification of COVID-19 disease severity at baseline. Guidance to study subjects for grading of signs and symptoms will be based on definitions used for the grading of TEAEs:

- None (Grade 0): Not present
- Mild (Grade 1): Symptoms that are usually transient and may require only minimal or no palliative or specific therapeutic intervention and generally do not interfere with the subject's usual activities of daily living.
- Moderate (Grade 2): Symptoms that are usually alleviated with palliative or specific therapeutic intervention. The symptoms interfere with usual activities of daily living causing discomfort but pose no significant or permanent risk of harm to the study subject.
- Severe (Grade 3): Events interrupt usual activities of daily living, or significantly effect clinical status, or may require intensive therapeutic intervention. Severe events are usually incapacitating.

A subject who meets any of the following criteria will be **excluded** from participation in this study:

1. Positive urine pregnancy test at screening or females who intend to become pregnant during the study.
2. COVID-19 signs associated with severe respiratory distress or imminent serious medical outcomes.^{^^}

^{^^}Potential Study Subjects Presenting with any of the following should be referred for immediate medical care and are not eligible for the study

- Fever > 104° F
- Cough with sputum production
- Rales and/or rhonchi
- Difficulty breathing with respiratory distress defined by a respiratory rate ≥ 30 per minute, heart rate ≥ 125 per minute, SpO₂ $\leq 93\%$ on room air at sea level or PaO₂/FiO₂ < 300 .
- Persistent pain or pressure in the chest
- Confusion

3. Any medical disease or condition that, in the opinion of the site Principal Investigator (PI) or appropriate sub-investigator, precludes study participation.
5. Reports a recent positive test result (within the past 6 months) for hepatitis A, hepatitis B or,

hepatitis C virus antibody, or HIV-1 antibodies at screening.

6. Has a history of alcohol abuse or other recreational drug (excluding cannabis) use within 1 month of Study Day 1.
7. Currently enrolled in or plans to participate in another clinical trial with a therapeutic investigational agent (e.g., monoclonal antibody, oral protease inhibitor) that will be received during the study period.
8. History of systemic antiviral therapies (e.g., remdesivir) within the past 30 days.
9. History of oral or parenteral corticosteroid use within the past 30 days. Active use of nasal or inhalable steroids is also exclusionary. Topical steroids are not exclusionary.
10. Has a history of hypersensitivity or severe allergic reaction (e.g., anaphylaxis, generalized urticaria, angioedema, other significant reaction) to sun exposure.
11. Currently undergoing photodynamic therapy (PDT) or photochemotherapy (PUVA) for an unrelated disease or condition that utilizes photosensitizing drugs including but not limited to 5-aminolevulinic acid, Methyl-5-aminolevulinic acid, porfimer sodium, methoxsalen (8-methoxypsonal), 5-methoxypsonal, trioxsalen.
12. Has any oral abnormality including ulcer, oral candidiasis, oral mucositis, gingivitis, burning mouth syndrome, dry mouth syndrome, a disease that can result in xerostomia (e.g. Sjogren's syndrome), or other oral disorder that in the opinion of the investigator would interfere with device use and evaluation.
13. Any intra-oral body piercings that cannot be removed and remain removed for the duration of the study. Metal orthodontia is permitted as braces will be covered by the device mouthpiece.
14. Any individual without teeth or with a dental malformation that precludes directed use of the device as intended.

4.3 Study Schedule of Activities

| Study Procedures | Screening, Enrollment & Randomization | Follow-up Period (Visit Window) | | | | | | |
|---|---|------------------------------------|-------------------------------------|-------------------------------------|-------------------------------------|-------------------------------------|-------------------------------------|-------------------------------------|
| | | 1 @ Each Study Day | 2 | 3 | 4 | 5 (-1 to +1) | 8 (-1 to +1) | 14/ET (-2 to +2) |
| Informed Consent | | X | | | | | | |
| COVID-19 Testing - SARS-CoV-2 Rapid Antigen Test* | | X | | | | | X | X |
| Medical History & Physical Examination | | X | | Changes since last visit only | | Changes since last visit only | X | X |
| Oropharyngeal Assessment | | X** | | Changes since last visit only | | Changes since last visit only | X | X |
| Urine Pregnancy Test | | X | | | | | | |
| Concomitant Medication History/New | Baseline | | Changes since last visit only | | Changes since last visit only | Changes since last visit only | Changes since last visit only | Changes since last visit only |
| Blood Draw (CMP, CBC, SARS-CoV-2 antibody) | | X | | | | | | X |
| Methemoglobin | | X | | | | | | X |
| Vital Signs | | X | | X | | X | X | X |
| Adverse Event Assessment / Reactogenicity | Baseline | | X | | X | X | X | X |
| Demographics, Inclusion / Exclusion Review | | X | | | | | | |
| Diary Dispensation (Diary Card Training) / Collection | | X | | | | X | X | X |
| Dispense RD-X19 Device / Treatment at Site*** | | X | | X | | X | | |
| SARS-CoV-2 Biospecimen collection for viral assays (2 specimens – saliva and nasopharyngeal swab)**** | | X | | X | | X | X | X |
| Extra saliva specimen collection for exploratory oral microbiome assessment | | X | | | | | X | X |
| COVID-19 Disease Assessment | | X | | | | | X | X |
| Telephone Call for Safety Monitoring and Compliance | | | X | | X | | | |
| Collect RD-X19 Device | | | | | | | X | |

* Subjects presenting at the time of screening that have tested positive via a SARS-CoV-2 rapid antigen test at or within the past 24 hours of the screening visit and can provide documentation confirming proper identification, the date of the test and testing location, positivity of the result, and name/identity of the assay used to generate the result, are also eligible for enrollment and the rapid antigen test does not have to be repeated at the site.

** On Day 1 to be evaluated 30 minutes after first illumination at site.

*** For scheduling purposes, the recommended interval between treatment is not < 6 hours.

Only one treatment of the twice daily regimen will be done on site on Days 1, 3 and 5, the second treatment will be done at home. For Day 1, the subject will be instructed to complete two treatments regardless of time of enrollment (e.g. 4 pm and 10 pm).

**** At Baseline and days 3, 5, 8, and 14, subjects will provide one saliva specimen and one nasopharyngeal swab for virology endpoint assessments. Biospecimens will be collected, preserved, and shipped to a central lab for assessment of SARS-CoV-2 mRNA via RT-qPCR. Optionally, the sponsor may perform additional genetic sequencing on one or both baseline specimens to obtain incidence of CDC classified variants of concern in the study population.

5 INTRODUCTION

5.1 Background and Study Rationale

In laboratory studies, the LED technology employed in the RD-X19 device has demonstrated the ability through both direct and intermediate mechanisms, to kill cell-free virus by as much as 99.99% and inhibit cell-associated replication of multiple coronaviruses by 99.9% when measured at 24 hours after a single light treatment in vitro. The technology utilized by RD-X19 has been repeatedly demonstrated to provide dose-dependent antiviral activity in multiple, laboratory in vitro modelss. The mechanism of action, direct cell-free killing of virus by 425nm visible blue light and an augmented innate immune response presents an breakthrough opportunity for therapy that is not specific pathogen-directed or dependent on antigen-specific adaptive immunity.

5.2 Risk/Benefit Assessment

5.2.1 Known Potential Risks

The potential risks of participating in this trial are those associated with having blood drawn and mild, transient, local reactions as measured in EB-P10-01, a Phase I Open Label, Acute Safety Study of the EmitBio RD-X19 Device in healthy adults. There were no SAEs, TEAEs (including local reactions) attributed in EB-P12-01, a Phase I/II randomized, sham controlled, double-blinded trial in indivuals with mild to moderate COVID-19. See the Clinical Investigators Brochure for more detail.

Drawing blood may cause transient discomfort and fainting. Fainting is usually transient and managed by having the subject lie down and elevate his/her legs. Bruising at the blood draw site may occur but can be prevented or lessened by applying pressure to the blood draw site for a few minutes after the blood is taken.

Extensive evaluation of the RD-X19 and similar energy-based devices routinely used for oral and skin care purposes resulted in the Sponsor, after careful consideration, making the determination that RD-X19 ia a “Not Significant Risk” (NSR) device per FDA guidelines. This was affirmed twice by protocol Institutional Review Boards (IRBs).

CAUTION - The light emitted may be harmful to the eyes. Do not stare at the light. Photobiological eye safety testing has classified this device as Risk Group 2 - Moderate risk. The blue light emitted does not pose an immediate hazard due to aversion response to very bright light sources or due to thermal discomfort of prolonged exposures. However, direct illumination of unprotected eyes should be avoided. Study staff must ensure volunteers understand to never point the RD-X19 device toward their or anyone else's eyes.

A summary of the known and potential risks of the RD-X19 are as follows:

- Depth of insertion beyond recommended depth has the potential to result in pharyngeal gag reflex for some study subjects.

- Exposure to blue light may be harmful to the eyes when the device is used incorrectly.
- Overexposure of tissues to blue light can cause mild, transient pharyngeal discomfort and erythema.
- Extended blue light exposure to eyes may result in worsened headache pain associated with chronic migraines and other cerebral vascular disorders associated with headache.
- Shining the end of the RD-X19 illumination device directly onto skin, approximately 1 cm away has the potential to induce mild erythema.
- Elimination of oral microflora with blue light has the potential to lead to oral candidiasis and/or disruption of the oral microbiome.

Risks to Privacy

Subjects will be asked to provide personal health information (PHI). All attempts will be made to keep this PHI confidential within the limits of the law. However, there is a chance that unauthorized persons will see the subject's PHI. All study records will be kept in a locked file cabinet or maintained in a locked room at the participating clinical trial site(s). Electronic files will be password protected. Only people who are involved in the conduct, oversight, monitoring, or auditing of this trial will be allowed access to the PHI that is collected. Any publications from this trial will not use information that will identify subjects by name.

Organizations that may inspect and/or copy research records maintained at the participating clinical trial site(s) for quality assurance (QA) and data analysis include groups such as the IRB and the FDA.

A description of this clinical trial will be posted on <http://www.ClinicalTrials.gov>. This web site does not include information that can identify subjects.

There may be other risks, discomforts or side effects that are entirely unknown at this time.

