9.2.2 Solicited Treatment Emergent Adverse Events - Reactogenicity

Solicited TEAEs are anticipated TEAEs for which consistent collection of information is desired. Study clinicians will follow and collect resolution information for any reactogenicity symptoms that are not resolved during the active study period.

Solicited TEAEs (i.e., reactogenicity) will be collected by direct questioning of study subjects and recorded on the appropriate source document and e-CRF during the entire course of the study.

For this study, solicited AEs include:

- Illumination site Pain
- Illumination site Erythema
- Illumination site Edema/Induration
- Any other pain, redness, swelling or lesion of the oral mucosa

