### 5.6.2 Reactogenicity Assessments

Tabulations will be generated by study visit for reactogenicity with number and percentage of subjects who experienced illumination site reactions (pain, erythema, edema/induration, and other pain, redness, swelling, or lesion of the oral mucosa).

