O:\Studies\EmitBio\EB-P20-01\Biometrics\Programs\Tables\xxx.sas ran on Month Day, Year at hh:mm on data from Month Day, Year.

Table 14.3.1.4 –Treatment-Emergent Adverse Events by System Organ Class, Preferred Term and Study Day of Most Severe Observation for Safety Population

System Organ Class Preferred Term	Study Day*	RD-X19 from Final Cohort (N=XX) n (%)	RD-X19 from Cohort A (N=XX) n (%)	Pooled RD-X19 (N=XX) n (%)	Pooled Sham (N=XX) n (%)
Subjects Reporting at Least One Adverse Event	Day 1	XX (XX.X)	XX (XX.X)	XX (XX.X)	XX (XX.X)
	Day 2	XX (XX.X)	XX (XX.X)	XX (XX.X)	XX (XX.X)
	...				
System Organ Class #1	Day 1	XX (XX.X)	XX (XX.X)	XX (XX.X)	XX (XX.X)
	Day 2	XX (XX.X)	XX (XX.X)	XX (XX.X)	XX (XX.X)
	...				
Preferred Term #1	Day 1	XX (XX.X)	XX (XX.X)	XX (XX.X)	XX (XX.X)
	Day 2	XX (XX.X)	XX (XX.X)	XX (XX.X)	XX (XX.X)
	...				
...					
...					

\*Study Day is calculated relative to date of first treatment. Day 1 is the day of first treatment. For the summary, Study Day is the day number when the most severe observation was made of an event.

Counts reflect numbers of subjects reporting one or more TEAE that map to the MedDRA system organ class/preferred term. At each level of summarization (system organ class or preferred term), subjects reporting more than one TEAE are counted only once under the earliest Study Day when the event of greatest severity was reported.

Source: Listing 16.x.x

O:\Studies\EmitBio\EB-P20-01\Biometrics\Programs\Tables\xxx.sas ran on Month Day, Year at hh:mm on data from Month Day, Year.

Table 14.3.2 – Reactogenicity by Visit for Safety Population

Study Visit	Category	RD-X19 from Final Cohort (N=XX)	RD-X19 from Cohort A (N=XX)	Pooled RD-X19 (N=XX)	Pooled Sham (N=XX)
Visit 1 / Day 1	N	XX	XX	XX	XX
	n (%) subject with any findings on reactogenicity assessment	XX (XX.X)	XX (XX.X)	XX (XX.X)	XX (XX.X)
	n (%) subject with illumination site pain	XX (XX.X)	XX (XX.X)	XX (XX.X)	XX (XX.X)
	n (%) subject with illumination site erythema	XX (XX.X)	XX (XX.X)	XX (XX.X)	XX (XX.X)
	n (%) subject with illumination site Edema/Induration	XX (XX.X)	XX (XX.X)	XX (XX.X)	XX (XX.X)
	n (%) subject with other pain, redness, swelling, lesion of the oral mucosa	XX (XX.X)	XX (XX.X)	XX (XX.X)	XX (XX.X)
Visit 2 / Day 3	N	XX	XX	XX	XX
	n (%) subject with any findings on reactogenicity assessment	XX (XX.X)	XX (XX.X)	XX (XX.X)	XX (XX.X)
	n (%) subject with illumination site pain	XX (XX.X)	XX (XX.X)	XX (XX.X)	XX (XX.X)

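### Eye harm, gag reflex and skin erythema are listed device risks, but none is specifically solicited or given its own row in the reactogenicity table, which weakens the capture of brief events during home treatment.

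*Protocol*

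**What the plan says.** Protocol Section 5.2.1 gives a caution about the eyes, with a Risk Group 2 (moderate) photobiological classification, and then lists six known or potential risks. Three of them matter here:

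- Eyes: "Exposure to blue light may be harmful to the eyes when the device is used incorrectly".
- Gag: "Depth of insertion beyond recommended depth has the potential to result in pharyngeal gag reflex for some study subjects".
- Skin: "Shining the end of the RD-X19 illumination device directly onto skin, approximately 1 cm away has the potential to induce mild erythema".

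Protocol Section 9.2.2 describes solicited events as those that are expected and on which uniform information is wanted. It names four: illumination site pain, illumination site erythema, illumination site edema or induration, and "Any other pain, redness, swelling or lesion of the oral mucosa". Section 4.1.2 fixes where the illumination site is: "Light will be administered locally to the mouth and throat only".

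The SAP carries the same four items forward. Section 5.6.2 tabulates "illumination site reactions (pain, erythema, edema/induration, and other pain, redness, swelling, or lesion of the oral mucosa". Table 14.3.2 has a row for any finding and one row per item, the last being "subject with other pain, redness, swelling, lesion of the oral mucosa". The reaction columns of Listing 16.2.9.3 are the same four.

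Everything else falls under Protocol Section 9.2.3, which records events that the subject reports unprompted, that come up in answer to an open question, or that observation, examination or another diagnostic procedure reveals.

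**The concern.** By the protocol's own description, an event is solicited because it is anticipated and should be collected consistently. The three harms above are anticipated, since the risk section names them. Another risk on the same list, pharyngeal discomfort and erythema from overexposure, is solicited through the illumination-site items. The documents give no reason for treating the eye, gag and skin risks differently.

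The trial sets out to provide evidence of safety for a selected dose (Protocol Section 4.1.1), and device-related adverse events feed the decisions on cohorts and on pausing (Sections 4.1.2 and 8.5.1). If a known hazard is never asked about by name, a low count is hard to read: it may mean that the event is rare, or that brief episodes were forgotten or not thought worth mentioning. The comparison with sham suffers too, because both arms depend on the same open-ended recall.

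**Working it through.** **Listed risks against means of capture.** The six risks in Protocol Section 5.2.1, and where each is specifically looked for:

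| Listed risk | Specific means of capture |
|---|---|
| Gag reflex from over-insertion | None |
| Eye harm from incorrect use | None |
| Pharyngeal discomfort and erythema | Solicited: illumination site pain, erythema |
| Worsened headache after extended eye exposure | Diary symptom, scored twice daily, though mixed with COVID-19 headache |
| Erythema of skin exposed to the light | None |
| Oral candidiasis or microbiome disruption | Oropharyngeal assessment and oral examination |

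Of the four solicited items, none names the eyes, gagging or skin away from the mouth and throat.

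**Number of treatments taken at home.**

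- Scheduled treatments: 2 per day × 7 days = 14. This reproduces the 14 in the per-protocol rule of Protocol Section 10.3, where 75% of 14 is 10.5, rounded up to 11.
- On site: one treatment on each of Days 1, 3 and 5 (note to the schedule in Protocol Section 4.3), so 3. SAP Listing 16.2.5.1 records supervision for those visits only.
- At home: 14 − 3 = 11, and 11/14 = 78.6%. That this equals the per-protocol threshold of 11 is a coincidence.

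**What the unsolicited route offers, and when.**

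- Interim history by interview at every later visit, and full examinations including skin and head, ears, eyes, nose and throat at screening, Day 8 and Day 14 (Protocol Section 9.2). The two later examinations are nominally after the 7-day treatment course. On Days 3 and 5 the schedule asks only for changes, with a targeted examination if indicated.
- Calls on Days 2 and 4, at which adverse events are documented (Section 9.2).
- Observation for at least 30 minutes after the first illumination (Section 9.2).
- After the Day 5 visit the next scheduled contact is Day 8. If the Day 5 site treatment is the first of that day, 1 (Day 5) + 2 × 2 (Days 6 and 7) = 5 home treatments fall in that interval.
- The diary is reviewed for possible adverse events. Its described content is the eight symptoms, temperature, oxygen saturation, shortness of breath and treatment count (Sections 6.3 and 9.2), with no field for eye, gag or skin events.

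A gag or a short visual disturbance at home leaves nothing to see at a later examination, and mild redness of skin may also have faded. Such events then depend on the subject recalling them in answer to a general question.

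**Size.** An under-count would be the true event rate multiplied by the share of events missed. The documents give neither quantity, so no figure can be derived.

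**The case against.** The strongest objection is that the plan does have ways to find these events. A reader might infer from the solicited list that eye, gag and skin harms are counted only if the subject volunteers them. The documents do not support that: there are open questions, interviews at every later visit, two telephone calls and examinations of eyes and skin. SAP Section 5.6.1 tabulates all treatment-emergent events, solicited or not. A reported eye or skin event that is related and of Grade 2 or higher also counts under the pausing rule without having been solicited, because that rule is not limited to local reactions. This part of the objection stands, and it limits the point to the absence of a targeted question and a dedicated row.

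It can also be said that the three risks depend on incorrect or off-target use, which the plan addresses by instruction, by supervised site treatments and by possible removal for misuse, so soliciting reactions at the intended site is a defensible focus. That is fair, but misuse is least visible at home, where most treatments occur.

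A second tempting inference is that a device-provoked gag would be scored as nausea and so disturb the primary endpoint. Nothing in the documents says so. Mild scores are compatible with resolution, and a visit question about gagging would not relabel diary scores. It is no part of this point.

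Finally, the reactogenicity form, the adverse event form and the diary card are not reproduced. They may contain prompts that the protocol list and the SAP shells do not show.

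**Conclusion.** The point holds in a limited form. Three risks that the protocol itself lists are neither specifically solicited nor separately tabulated in the reactogenicity table. They can enter the record as unsolicited events, and those events are tabulated, but that route is weaker for transient events in the 11 of 14 treatments taken at home. The amount of under-reporting cannot be computed from the documents, and any figure would rest on an assumed capture rate. A reader should not conclude that the safety data would miss these harms altogether, nor that the pausing rule ignores them.

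The conclusion assumes that the forms follow the list in Protocol Section 9.2.2 and the SAP shells, and that subjects follow the planned schedule of treatments and visits. It concerns ascertainment only and bears on no dose or clinical rule. It is a worthwhile, inexpensive improvement, not a flaw that undermines the trial.

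**What to change.** Add three yes/no items to the reactogenicity assessment in Protocol Section 9.2.2:

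- eye discomfort or visual disturbance;
- gagging or retching during treatment;
- redness of skin exposed to the light.

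Ask them at each post-baseline visit about all treatments since the previous visit, including those at home, and on Day 1 about the site treatment. Name the items in SAP Section 5.6.2, and add matching rows to Table 14.3.2 and columns to Listing 16.2.9.3, shown by RD-X19 dose and for sham.

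The cost is three short questions on an assessment already scheduled, plus a few rows and columns. The downside is slightly more mild events reported in both arms.

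SAP Section 3.1 describes the expansion of the Final Cohort in the past tense, so a changed form may reach only later subjects. In that case, report which subjects were asked. For everyone, pre-specify before unblinding a grouped summary of eye, gagging or retching, and skin events drawn from the adverse event data. That summary would make the reported events easy to see, but it cannot recover events that were never asked about.
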